3. SAMPLE SIZE DETERMINATION

Determination of sample size is based on participants enrolled in the global enrollment phase. In each study, approximately 1016 participants will be enrolled and randomized in 1:1 ratio to each treatment arm (active drug or placebo) during the global enrollment phase. The original planned sample size was of 760 participants, but it was increased to 1016 participants based on considerations from external studies (in protocol version 3).

Additional participants may be randomized during the China extension if at least 1 participant is enrolled at sites in mainland China, Hong Kong, or Taiwan that are recognized by the NMPA during the global enrollment phase.

The estimated sample size required to demonstrate efficacy with regard to Clinical Dementia Rating-Sum of Boxes (CDR-SB) is based on the following assumptions:

- the mean change in the CDR-SB from baseline to Week 104 is 2.5 points in the placebo arm
- a common standard deviation across treatment arms for change of approximately 2.97 from baseline to Week 104 in the CDR-SB
- active drug has a true effect of a 30% relative reduction in deterioration of CDR-SB

Based on these assumptions, and using a student's T-test with equal variance, a sample size was calculated for 90% power to detect a true treatment effect of 30% relative reduction in deterioration of CDR-SB at a two-sided α of 0.05.

Uncertainties on parameters affecting the power (e.g., dropout rate, study drug discontinuation rate, standard deviation, and placebo decline) were assumed to be equivalent to a drop in sample size of up to around 35% and were corrected for accordingly. This calculation leads to a total of 1016 participants in the study.

At the date of writing Protocol Version 4, it was expected that participants would miss an average of 8 weeks of study drug administration over the course of the original two-year study due to the COVID-19 pandemic. This had the potential to decrease the power of the study from ~90% to ~80%. To mitigate the impact of missed administrations, the double-blind treatment period has been extended by 12 weeks. Under current assumptions, this brings the study power back to the originally planned ~90%.

4. ANALYSIS SETS

The following analysis sets are defined:

Table 2 Analysis Sets

| Analysis set | Definition | Scope |
|---|---|--|
| All enrolled participants | All participants randomized during the global enrollment phase whether or not the participant received the assigned treatment. Analysis using this analysis set will be performed by randomized treatment. | Participant disposition report will be based on this analysis set |
| Intent-to-treat (ITT) | All participants randomized during the global enrollment phase, who received at least one dose of study drug. Analysis using this analysis set will be performed by randomized treatment. | All efficacy analyses, including the primary estimand, will be based on this analysis set. |
| CSF modified intent-to-treat (CSF-mITT) | All participants in the ITT analysis set who had at least one valid quantitative cerebrospinal fluid (CSF) measurement Analysis using this analysis set will be performed by randomized treatment. | All analyses of CSF biomarkers will be based on this analysis set |
| CSF-longitudinal | All participants in the CSF-mITT who had at least one valid quantitative Week 116 CSF measurement of phosphorylated tau (pTau-181), tTau, Neurogranin or NFL. | Summary of treatment group comparability will also be repeated on this analysis set. |
| Plasma-longitudinal | All participants in the ITT analysis set who had at least one valid quantitative post-baseline plasma measurement of Amyloid beta (1-42) (Aβ ₄₂) or phosphorylated tau (pTau-181) | Summary of treatment group comparability will also be repeated on this analysis set. |
| MRI modified intent-to-treat (MRI-mITT) | All participants in the ITT analysis set who had at least one valid volumetric MRI quantitative measurement. Analysis using this analysis set will be performed by randomized treatment. | All analyses of volumetric MRI parameters will be based on this analysis set. |
| MRI-longitudinal | All participants in the MRI-mITT with at least one valid post-baseline volumetric MRI quantitative measurement. | Summary of treatment group comparability will also be repeated on this analysis set. |
| Tau PET modified intent-to-treat (Tau-PET-mITT) | All participants in the ITT analysis set who participated in the Tau PET sub-study and who had at least one Tau PET scan with a valid quantitative measurement and who did not withdraw from the Tau PET substudy before randomization Analysis using this analysis set will be performed by randomized treatment. | All analyses of Tau PET parameters will be based on this analysis set. |
| Tau-PET-longitudinal | All participants in the Tau-PET-mITT with a valid post-baseline quantitative Tau PET measurement. | Summary of treatment group comparability will also be repeated on this analysis set. |

Table 2 Analysis Sets (cont.)

| Analysis set | Definition | Scope |
|---|--|--|
| Amyloid PET modified intent-to-treat (Amyloid-PET-mITT) | All participants in the ITT analysis set who participated in the Amyloid PET sub-study and who had at least one Amyloid PET scan with a valid quantitative measurement performed with either florbetaben or flutemetamol and who did not withdraw from the Amyloid PET substudy before randomization. | All analyses of Amyloid PET parameters will be based on this analysis set |
| Amyloid-PET-longitudinal | Analysis using this analysis set will be performed by randomized treatment. All participants in the Amyloid-PET-mITT with a valid post-baseline quantitative amyloid PET measurement performed with either florbetaben or flutemetamol. | Summary of treatment group comparability will also be repeated on this analysis set. |
| Safety-evaluable | All participants randomized during the global enrollment phase who received at least one dose of study drug. Any participant randomized to placebo who received at least one dose (any dose) of active drug will be summarized as having received the active drug. Analysis using this analysis set will be performed by treatment actually received. | All safety analyses (with the exception of Safety MRI) will be based on this analysis set. |
| MRI Safety-evaluable | All participants in the Safety-evaluable analysis set who had at least one post-baseline safety MRI scan. Analysis using this analysis set will be performed by treatment actually received | All analyses of safety MRI will be based on this analysis set. |
| Amyloid-PET Safety Evaluable | All participants in the Safety-evaluable analysis set who received at least one dose of radioligand Analysis using this analysis set will be performed by treatment actually received | All safety analysis for the amyloid-PET sub-study will be based on this analysis set. |
| Tau-PET Safety Evaluable | All participants in the Safety-evaluable analysis set who received at least one dose of radioligand. Analysis using this analysis set will be performed by treatment actually received | All safety analysis for the tau-PET sub-study will be based on this analysis set. |

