## **6. STATISTICAL CONSIDERATIONS AND ANALYSIS PLAN**

The purpose of this study is to investigate the treatment effect of gantenerumab relative to placebo. The primary efficacy analysis will be based on an intent-to-treat (ITT) population, which will include all randomized participants during the global enrollment phase, with participants grouped according to their randomly assigned treatment.

Approximately 1016 participants will be randomized in the global enrollment phase of this study. An increase in sample size may be considered in case of changes to sample size assumptions based on blinded data review or factors external to the study.

If at least 1 participant is enrolled at sites in mainland China, Hong Kong, and Taiwan that are recognized by the NMPA during the global enrollment phase, additional participants may be enrolled in a China extension to ensure a total enrollment that is sufficient to support registration in the China.

The primary analyses of this study will include participants enrolled during the global enrollment phase; data from participants enrolled during the China extension will not be included in the primary analyses.

*Details of the planned statistical analyses mentioned below will be fully specified in a separate SAP, which will be finalized prior to the locking and unblinding of the study database.*

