### **6.4.1 Primary Efficacy Endpoint**

The primary efficacy outcome measure is the change in CDR-SOB from baseline (Day 1) to Week 116. In the case where the double-blind treatment period is extended for an additional 12 weeks, the primary efficacy outcome measure will be the change in CDR-SOB from baseline (Day 1) to Week 128.

*The clinical question of interest is to assess the study treatment effect on disease progression up to Week 116 (or Week 128, if applicable), irrespective of use or initiation of symptomatic treatments for AD, in the absence of the COVID-19 pandemic.*

*In accordance with the estimand framework outlined in the ICH-E9 addendum (EMA 2018), the attributes of the estimand for the primary endpoint are defined as follows:*

- *Population: early (prodromal to mild) AD population including all randomized participants.*
- *Variable: change from baseline at Week 116 (or Week 128) in the CDR-SOB*
  - *Treatment: prescribed study drug including up-titration to the target dose, irrespective of use or initiation of symptomatic treatment for AD.*
- *Intercurrent events (ICE): the list of ICE will be defined in the SAP, this includes:*
  - *Treatment discontinued for study drug or condition-related (SDCR) reasons (e.g., treatment-related adverse event or lack of efficacy):*

- *Treatment discontinued for non-SDCR (NSDCR) reasons (e.g. purely administrative reason)*
- *Population level summary: mean change from baseline to Week 116 (or Week 128, as appropriate) between gantenerumab-treated participants and placebo-treated participants.*

*The primary estimand is a combination of a treatment-policy strategy and a hypothetical strategy (FDA 2017) to account for the different assumptions for each type of ICE, SDCR or NSDCR.*

*Full details of the primary estimand, and of the corresponding estimator and estimation methods (e.g. statistical model, multiple imputation for missing or excluded data points) will be provided in the SAP. Supplementary estimands may also be considered and will be defined in the SAP.*

Every effort will be made to minimize missing data. Furthermore, the Sponsor *has made every effort to expedite the implementation of the 12 week extension to the double-blind treatment period.* If the study is extended by an additional 12 weeks (for a total extension of 24 weeks), the number of patients in scenario 1 (who will have missing Week 128 efficacy data) will be minimized.

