5.3.2 Definition of Primary Estimand

The clinical question of interest is to assess the effect of the active drug on disease progression at Week 116, irrespective of use or initiation of symptomatic treatments for AD, in the absence of a substantial impact of the COVID-19 pandemic.

In alignment with the Addendum to [ICH E9](#), the primary efficacy estimand is described by the following attributes:

- **Target Population:**
Early (prodromal to mild) AD population as identified by the inclusion and exclusion criteria, see Sections 4.1.1 and 4.1.2 of the study protocols
- **Variable:**
Change from baseline to Week 116 in Clinical Dementia Rating – Sum of Boxes (CDR-SB)
- **Treatment:**
Prescribed study drug including uptitration to the target dose and safety-related dose modifications, irrespective of use or initiation of symptomatic treatment for AD
- **Population-level summary:**
Difference in variable means between treatment arms

Intercurrent events (ICE):

The ICEs are classified into two categories: those that are Study Drug or Condition Related (SDCR) and those that are not (NSDCR). The list of main anticipated ICEs, and their classification as SDCR or NSDCR, is presented below ([Table 3](#)). The final list of ICEs may need to be adapted in case unanticipated ICEs emerge during the study conduct. The classification of each ICE into SDCR or NSDCR will be completed and documented prior to the unblinding.

The ICE of substantial reduction in drug exposure due to the COVID-19 pandemic is defined as 4 or more dose-months (i.e., 16 weeks, not necessarily consecutive) of treatment missed due to COVID-19-related reasons. This definition will be equally applied to placebo and active arms. One dose-month is defined as 4 weeks of dosing, i.e., one dose with a Q4W dosing frequency (mostly during uptitration) or two doses with a Q2W dosing frequency (at target dose). The threshold of four missed dose-months was determined based on the following reasons:

- A 12-week extension to the study was implemented (in protocol amendment version 4) to mitigate the impact of the COVID-19 pandemic. Therefore, treatment interruptions up to 3 dose-months (i.e., 12 weeks) are already accounted for in the study design.
- Based on the half-life of approximately 24 days of gantenerumab, plasma concentration after a 4 months' interruption at the target dose is expected to be below the observed concentration with the dose of 225 mg Q4W which was

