The primary estimator will be applied to the ITT analysis set (see Table 2) and it will be implemented using four steps. First, an imputation model will be fitted to the data. Second, imputation of missing data will be performed based on the parameter estimates from the imputation model. Third, the completed data will be analyzed using an analysis of covariance (ANCOVA) model. Finally, inference will be performed based on resampling techniques. All four steps are described and justified in a published manuscript (Wolbers et al. 2022) which provides a more detailed justification of the statistical methodology and supportive simulations. Considerations about the control of type-I error for the primary estimator and supportive simulations, mimicking the setting of the GRADUATE I and GRADUATE II studies and exploring an extended range of plausible scenarios for missing data, are provided in the Appendix 1.

1. Imputation model

The imputation model is a mixed effects model for repeated measures (MMRM) with the longitudinally assessed change from baseline in CDR-SB as the dependent variable. Its purpose is to estimate mean trajectories and covariance matrices of longitudinal outcomes in the placebo and active drug arms, respectively, while subjects remain on their randomized treatment. Therefore, all data after withdrawal from study treatment will be removed and considered as missing for the purpose of estimating the imputation model, and for this purpose only. If these data were not excluded, then the imputation model would estimate mean trajectories based on a mixture of observed pre- and post-discontinuation data. These would not be compatible with the CIR assumption employed in the subsequent imputation step, which requires combining mean trajectories while on active drug up to the ICE with increments while on placebo thereafter, respectively.

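### The SAP's ITT set requires at least one dose, whereas the protocol's ITT and primary estimand population is all randomised participants; no all-randomised analysis is planned

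*SAP*

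**What the plan says.** **Protocol.** Section 6 states: "The primary efficacy analysis will be based on an intent-to-treat (ITT) population, which will include all randomized participants during the global enrollment phase". Section 6.4.1 gives the population attribute of the primary estimand as "early (prodromal to mild) AD population including all randomized participants", and the synopsis agrees. The dosing condition appears only in section 6.5, for the safety population.

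**SAP.** Table 2 in section 4 defines ITT as "All participants randomized during the global enrollment phase, who received at least one dose of study drug". Its scope column reads: "All efficacy analyses, including the primary estimand, will be based on this analysis set". Section 5.3.3 confirms: "The primary estimator will be applied to the ITT analysis set". A separate set, All enrolled participants, is defined as "All participants randomized during the global enrollment phase whether or not the participant received the assigned treatment", but it is used only for disposition. The SAP's own estimand (section 5.3.2) describes the target population as "Early (prodromal to mild) AD population as identified by the inclusion and exclusion criteria", again without a dosing condition.

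The SAP introduction states that its language takes precedence over the protocol, so the dosed-only set is the one that will be analysed.

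**The concern.** Receiving a first dose happens after randomisation. Conditioning on it removes randomised people from the confirmatory comparison, and calling the result ITT tells readers of the study report that nobody was removed.

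This does not look like loose wording. The protocol distinguishes an undosed-inclusive ITT population from a dosed safety population. In the SAP the ITT and Safety-evaluable sets have the same membership rule and differ only in how participants are grouped. Elsewhere in Table 2, restricted sets are labelled modified ITT; this one is not.

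None of the sensitivity or supplementary analyses in sections 5.3.4 and 5.3.5 restores the excluded participants. The treatment-policy supplementary analysis keeps the population attribute unchanged. At stake is whether the reported population matches the protocol's estimand, in a test that decides the trial.

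**Working it through.** **1. The plan's own figure.** Inputs from SAP section 3 and protocol section 6.1: placebo change 2.5, SD 2.97, 30% relative reduction, two-sided alpha 0.05, power 90%, 35% allowance.

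- Planned difference: 0.30 × 2.5 = 0.75 points.
- Normal-approximation sample size for two means: 330 per arm. Inflated: 330 / 0.65 = 507.7, so 508 per arm and 1016 in total. This matches the plan. The t-test version gives 331 per arm, 510 after inflation, 1020 in total.
- Power with an effective 508 × 0.65 per arm: 90.1%.

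The sample size is not in dispute. These figures serve as the yardstick.

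**2. How many might be never dosed.** The documents give no figure for this trial. Protocol sections 1.2.2.2 and 1.2.2.3 report 797 treated of 799 enrolled and 387 treated of 389 enrolled.

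- 2/799 = 0.25%; × 1016 = 2.54 participants.
- 2/389 = 0.51%; × 1016 = 5.22 participants.

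A 2% rate (20.3 participants) is added below as a purely assumed upper case.

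**3. What restoring them would do to the estimate.** Under the primary estimator (SAP section 5.3.3), for given baseline covariates and no observed follow-up:

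- Placebo arm, or any event classified as not study drug or condition related (NSDCR): imputation is missing-at-random within the participant's own arm, so the arm mean is essentially unchanged.
- Active arm, event classified as study drug or condition related (SDCR): CIR from baseline gives the placebo mean change, so each such participant contributes a zero effect.

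The largest shift under imputation therefore has all *k* never-dosed participants in the active arm and all classified SDCR: shift = (*k* / 508) × 0.75, towards no effect.

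| Assumed rate | *k* | Shift (points) | Share of 0.75 |
|---|---|---|---|
| 0.25% | 2.54 | 0.004 | 0.5% |
| 0.51% | 5.22 | 0.008 | 1.0% |
| 2% (assumed) | 20.3 | 0.030 | 4.0% |

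An even split between arms halves each shift. The 0.75 is the planned Week 104 difference, used here as a stand-in for Week 116.

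**4. Power.** The percentages below are the assumed never-dosed share of each arm.

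| Never dosed | Excluded | Kept, with no effect in the active arm |
|---|---|---|
| 0.25% | 90.0% | 89.9% |
| 0.5% | 89.9% | 89.8% |
| 2% | 89.5% | 88.9% |

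The largest loss from the 90.1% baseline is about 1.2 points.

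**The case against.** **The SAP governs.** Protocol section 6.4.1 leaves the full detail of the estimand and estimator to the SAP, and the SAP takes precedence. This stands in one respect: what will be analysed is not ambiguous. It does not make a dosed-only set ITT or supply a reason for it, and the SAP's own target population carries no dosing condition either.

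**The condition has a practical use.** Baseline (section 5.1), study days and visit windows, and the rule placing assessments more than 28 days after the last dose beyond withdrawal (section 5.3.3) all depend on dosing. This also stands. A bare redefinition would leave these undefined for never-dosed participants, so the fix must supply rules.

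**The exclusions will be visible and are unlikely to depend on arm.** Disposition uses all enrolled participants, section 5.7.1 reports the size of each analysis set by arm, assignment is blinded, and analysis remains by randomised arm. This is right, and it is why the point is small.

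**Readings that go too far.**

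- *An undisclosed change.* A reader might infer this from the SAP's amendment table, which does not mention the restriction. That table covers only changes from version 2 to version 3; the definition may be older.
- *A shift large enough to matter.* Placing all never-dosed participants in one arm with 2.5 points of extra decline gives 5.22/508 × 2.5 = 0.026 points, or 3.4% of 0.75. The primary estimator cannot impute such values at given covariates; they would need observed follow-up of people who never started treatment.
- *A fault in the overlap with the Safety-evaluable set.* The two sets serve different purposes. The overlap only shows that the ITT label has lost its distinct meaning.

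**Conclusion.** The point holds. The primary analysis set does not meet the protocol's definition of ITT, the SAP text does not say why, and no planned analysis includes all randomised participants.

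Its numerical effect should be very small: at most about 0.004 to 0.008 points at Week 116 (0.5% to 1% of 0.75) at the earlier studies' rates, with power staying close to 90%. This rests on three assumptions: never-dosed rates like those studies, no observed follow-up in never-dosed participants, and a Week 116 effect near the planned 0.75.

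The documents do not support a claim of material bias or of concealed exclusions. The case for acting is that a post-randomisation exclusion can be removed from a confirmatory test at little cost.

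**What to change.** Before unblinding, define ITT in SAP Table 2 as all participants randomised in the global enrolment phase, analysed as randomised. For never-dosed participants, add these rules:

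- Use the randomisation date as Day 1 for baseline and visit windows.
- Treat all post-randomisation data as falling after the intercurrent event; the 28-day last-dose rule does not apply.
- Add an entry to Table 3 for never starting study treatment, classified SDCR or NSDCR by reason, with an uninformative reason taken as SDCR. Without this entry, their missing data count as unrelated to any intercurrent event and default to within-arm missing-at-random, which would impute undosed active-arm participants as though treated.
- Align the adjudication charter (SAP Appendix 3), which currently limits intercurrent events to those after treatment has begun.

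At minimum, rename the current set mITT, state the reason, and add an all-randomised sensitivity analysis of the primary endpoint under these rules.

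**Cost.** Edits to sections 4, 5.1 and 5.3, Table 3 and the charter; a check of the biomarker and imaging sets nested in ITT; a few fully imputed participants; and an estimate that may be very slightly less favourable. The CDR is scheduled at both screening and baseline, and section 5.1 allows screening as a fallback, so a primary-endpoint baseline should usually exist. ADAS-Cog13, ADCS-ADL and FAQ are not scheduled at screening, so a never-dosed participant without a baseline visit would still drop out of those secondary analyses.
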